Day	1	15	29	57	85	183	274	365	456	547	638	729		757	813	
Week	1	3	5	9	13	27	40	53	66	79	92	105		109	117	
Weeks elapsed since 1st dose	0	2	4	8	12	26	39	52	65	78	91	104		108	116	
Nominal months elapsed since 1st dose	0		1	2	3	6	9	12	15	18	21	24		25	27	
Procedures/ Assessments																

- b: Subjects who discontinue taking study drug prematurely for any reason will undergo an ED Visit within 7 days of their last dose of study drug. In addition, Follow-up Visits will be scheduled 4 and 12 weeks after the last dose of study drug (Visit 14 and Visit 15, respectively). Subjects who discontinue study drug before reaching 12 months of treatment will also be asked to return to the clinic for a 12 month clinical assessment and then again at 24 months. Subjects who discontinue treatment between 12 and 24 months of treatment will be asked to return to the clinic for a 24 month clinical assessment. Subjects who discontinue early from study drug are considered “on study” as long as they continue to return for their clinical assessments at 12 and 24 months as outlined above, at which efficacy (MMSE, CDR, ADAS- cog14) and quality of life (EQ-5D, QOL-AD and Zarit’s Burden Interview) will be assessed along with concomitant medications. New AEs will be collected for 4 weeks post last dose and followed-up for 12 weeks, or until resolution, whichever comes first. If >4 weeks post last dose only AEs relating to study procedures will be collected. These 12 and 24 month clinical assessment visits do not need to be attended if they fall within 8 days (visit window) after the ED Visit or within ±8 days of either of the Follow-up Visits (Visit 14 and Visit 15).

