investigation (eg, treatment-emergent infection), these samples may be tested to determine whether the subject already had prior exposure to any suspected infective agents. (revised per Amendment 03)

- n: The subject components of these assessments are to be completed in the morning whenever possible, or consistently at the same time of day. Ideally, the subject component of these assessments should be completed before more invasive assessments or procedures (eg, physical examination, ECG, blood draws). The FAQ is to be administered to the study partner. At visits where the CDR or FAQ are conducted, the investigator will determine whether the study partner must attend in person or whether telephone contact will be suitable, and will base this determination upon the functional ability of the subject among other factors.
- o: Disease staging will be performed every 3 months. The site clinician is required to confirm the staging of disease, ie for subjects who were, at Screening, not clinically staged as dementia, does the subject still meet the definition of MCI due to AD or have they progressed into the stage of clinical dementia. For any given subject, every effort should be made to ensure that the diagnosing clinician (responsible for the initial diagnosis and for disease staging) remains unchanged throughout the study. (revised per Amendment 03) This staging decision will be verified via a central review process and adjudicated if necessary. Adjudication will only occur when there is a discrepancy between the diagnosis and clinical disease staging made by the site compared to that determined by the central review process; moreover, where adjudication is required, it will be undertaken by an independent assessor(s).
- p: The clinical assessment of suicidality will require input from both the subject and the study partner
- q: There are 3 separate administrations of the EQ-5D as follows: (1) in the subject by self report, (2) in the study partner by self report, (3) in the subject by proxy using the study partner (revised per Amendment 01)
- r: There are 2 separate administrations of the QOL-AD as follows: (1) in the subject by self report, (2) in the subject by proxy using the study partner (revised per Amendment 01)

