9.5.5 Completion/Discontinuation of Subjects

A subject may elect to withdraw from the study at any time for any reason. All subjects who discontinue study drug early for any reason will undergo an ED Visit within 7 days of their last dose of study drug (see [Section 9.1.2.2](#)). In addition, Follow-up Visits will be scheduled 4 and 12 weeks after the last dose of study drug (Visit 14 and Visit 15, respectively) (see [Section 9.1.2.2](#)). These Follow-up Visits will be conducted to monitor efficacy and safety parameters after early withdrawal from the study or discontinuation of study drug. See [Table 5](#) for full details of the assessments to be performed at these visits.

All subjects who discontinue study drug before reaching 12 months of treatment will also be asked to return to the clinic for a 12 month clinical assessment and then again at 24 months. Subjects who discontinued treatment between 12 and 24 months of treatment will be asked to return to the clinic for a 24-month clinical assessment. Subjects who discontinue early from study drug are considered “on study” as long as they continue to return for their clinical assessments at 12 and 24 months as outlined above, at which efficacy and quality of life will be assessed along with concomitant medications and AEs. However, subjects who discontinue study drug early are not considered to have ‘completed’ the study as a final Subject Disposition. A subject removed from the study for any reason may not be replaced.

The investigator will promptly explain to the subject involved that the study will be discontinued for that subject and provide appropriate medical treatment and other necessary measures for the subject. A subject who has ceased to return for visits will be followed up by mail, phone, or other means to gather information such as the reason for failure to return, the status of treatment compliance, the presence or absence of AEs, and clinical courses of signs and symptoms.

The primary reasons for early withdrawal from the study are: AE, lost to follow up, subject choice, withdrawal of consent, pregnancy, study terminated by sponsor, and other. The secondary reasons for early withdrawal from the study are: AE, subject choice, and other.

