9.7.1.1.2 SECONDARY ENDPOINTS

The key secondary endpoints of the study are as follows (revised per Amendment 05):

- Change from baseline in ADCOMS at 24 months in the combined studies
- Change from baseline in amyloid PET SUVR at 24 months for brain amyloid levels in the combined studies
- Change from baseline in amyloid PET SUVR at 24 months for brain amyloid levels in the individual studies

The other secondary endpoints of the study are as follows (revised per Amendment 05):

- Change from baseline in the CDR-SB at 24 months for subjects enriched by baseline PET SUVR, eg, between 1.2 and 1.6, in the combined studies
- Change from baseline in the ADCOMS at 24 months for subjects enriched by baseline PET SUVR, eg, between 1.2 and 1.6, in the combined studies
- The rate of change over time (mean slope) based on CDR-SB score over 24 months in the combined studies
- Time to worsening of CDR scores by 24 months (eg, the worsening of global CDR score is defined as an increase from baseline by at least 0.5 points on the global CDR scale on 2 consecutive scheduled visits at which global CDR is undertaken) in the combined studies

- Time to conversion to dementia by 24 months for subjects who were not clinically staged as dementia at Baseline based on clinical diagnosis in the combined studies
- Change from baseline in CDR-SB at 27 months (ie, 24 months of treatment plus 3 months posttreatment follow-up) in the combined studies
- Change from baseline in ADAS-cog14, MMSE, and FAQ at 24 months in the combined studies
- Change from baseline in ADAS-cog14 Word List (immediate recall and delayed recall) at 24 months in the combined studies

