9.7.1.6.1 PRIMARY EFFICACY ANALYSIS

The primary analysis will be based on an intent to treat philosophy without regard to adherence to treatment. The primary analysis of the change from baseline in CDR-SB at 24 months will be performed to compare elenbecestat 50 mg per day versus placebo using a linear mixed effects model for repeated measures (MMRM) on the FAS. The MMRM model will include fixed effects of treatment group, visit, treatment group by visit interaction, baseline CDR-SB, baseline CDR-SB by visit interaction, and randomization stratification variables (ie, region [7 levels], clinical dementia [yes, no], and concurrent AD medication use at randomization [Visit 2] [yes, no]). *ApoE4* status may be included in the model if appropriate. (revised per Amendment 05) An unstructured covariance matrix will be employed to model the covariance of within subject effect; if MMRM fails to converge then a covariance structure with fewer parameters from the following list will be employed according to the prespecified order in the list until the MMRM converges. The list of covariance structure will include Heterogeneous Toeplitz, Toeplitz, Heterogeneous Compound Symmetry, and Compound Symmetry. This primary analysis will include all observed post baseline data of the change from baseline in CDR-SB without imputation of missing values. The treatment effect for elenbecestat versus placebo will be compared at

24 months based on MMRM model. The LS means and difference in LS means between elenbecestat treatment group and placebo, and corresponding 95% CI will be presented.

The null hypothesis is that there is no difference in the mean change from baseline in CDR-SB at 24 months between elenbecestat 50 mg per day and placebo. The corresponding alternative hypothesis is that there is a difference in the mean change from baseline in CDR-SB at 24 months between elenbecestat 50 mg per day and placebo.

The primary analysis will be repeated to minimize the impact of change in concomitant AD medications where efficacy data after initiation of new AD medications and increase of current AD medications will be censored.

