Time to worsening of CDR scores by 24 months will be analyzed on the FAS using Cox regression model for treatment effect adjusting for randomization stratification factors. ApoE4 status may be included in the model if appropriate. (revised per Amendment 05) Time to worsening of a CDR score is defined as time from randomization to worsening of the CDR score (ie, the first worsening in 2 consecutive scheduled visits). For subjects whose CDR scores have not worsened by the end of the Treatment Period of the Core Study, the time to worsening of the CDR score will be censored at the date of last CDR assessment for these subjects.

Time to conversion to dementia for subjects who were not clinically staged as dementia at Baseline based on clinical diagnosis will be analyzed on the FAS using Cox regression model for treatment effect adjusting for randomization stratification factors. ApoE4 status may be included in the model if appropriate. (revised per Amendment 05) Proportion of subjects with dementia diagnosis at 24 months will be estimated using Kaplan—Meier method based on time to conversion to dementia based on clinical diagnosis. Time to conversion to dementia for subjects who were not clinically staged as dementia at Baseline based on clinical diagnosis is defined as time from randomization to conversion to dementia based on clinical diagnosis. For subjects without clinical dementia by the end of study, the time to conversion to dementia based on clinical diagnosis will be censored at the date of last dementia diagnosis.

The other continuous secondary efficacy endpoints as defined above will be analyzed using the same MMRM model as the primary efficacy analysis to compare elenbecestat 50 mg per day versus placebo on the FAS, using baseline value corresponding to the response variable in the model.

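### Table 5 footnote b leaves FAQ and disease staging out of the 12- and 24-month return visits of subjects off drug, so two other-secondary endpoints lose late data that would be cheap to collect

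*Protocol*

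**What the plan says.** Footnote b of Table 5 (schedule for the Randomization Phase, revised per Amendments 04 and 05) asks subjects who stop drug early to return at 12 and 24 months, or at 24 months only if they stop after month 12. It names the content of those visits: "at which efficacy (MMSE, CDR, ADAS- cog14) and quality of life (EQ-5D, QOL-AD", then Zarit's interview and concomitant medications. Section 9.5.5 describes the same visits without a list: "at which efficacy and quality of life will be assessed along with concomitant medications and AEs".

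Two items absent from the footnote feed endpoints in Section 9.7.1.1.2, both classed as other secondary: "Change from baseline in ADAS-cog14, MMSE, and FAQ at 24 months in the combined studies" and "Time to conversion to dementia by 24 months for subjects who were not clinically staged as dementia at Baseline". Under Section 9.7.1.6.2, FAQ is covered by the sentence "The other continuous secondary efficacy endpoints as defined above will be analyzed using the same MMRM model as the primary efficacy analysis", on the FAS. Time to dementia is analysed by Cox regression on the FAS; subjects without dementia "will be censored at the date of last dementia diagnosis". For subjects on schedule, Table 5 footnote o states: "Disease staging will be performed every 3 months".

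**The concern.** Return visits for subjects off drug exist so that outcomes are observed whether or not treatment continued. Here the visit takes place and the CDR is done with study-partner input, yet two measures that feed secondary endpoints are not on the list, while three scales that feed only exploratory endpoints (EQ-5D, QOL-AD, Zarit) are.

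Two things are at stake. First, FAQ, MMSE and ADAS-cog14 share one endpoint bullet and one model, but at Month 24 only the latter two would include observed values from returning stoppers; for FAQ the model has to infer them. Second, in the dementia analysis a stopper's follow-up ends at the last staging. If stopping is related to decline or to tolerability, that censoring may be informative, and the 24-month Kaplan-Meier proportion with dementia is exposed to the same problem. An analysis plan cannot recover values that were never collected.

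**Working it through.** **Passages side by side** (Table 5 grid, footnote b, Section 9.7.1.1)

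| Measure | Endpoint level | On schedule at Visits 9 and 13 | Scheduled after stopping | Listed for 12-/24-month return |
|---|---|---|---|---|
| CDR | primary | yes | ED, Visits 14 and 15 | yes |
| MMSE, ADAS-cog14 | other secondary | yes | ED, Visits 14 and 15 | yes |
| FAQ | other secondary | yes | ED, Visits 14 and 15 | **no** |
| Disease staging | other secondary | yes | ED and Visit 15 | **no** |
| EQ-5D, QOL-AD, Zarit | exploratory | yes | ED | yes |

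Visit 15 is 12 weeks after the last dose. A subject who stops at about Day 183 (Month 6) has Visit 15 near Day 183 + 84 = 267. CDR, MMSE and ADAS-cog14 are then observed again at Months 12 and 24. FAQ and staging are not, which leaves 729 − 267 = 462 days unobserved.

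**The plan's sample size** (Section 9.7.2). The difference is 0.25 × 1.46 = 0.365, with SD 2.05, two-sided alpha 0.05 and 90% power. This gives 663 per arm; 663 / 0.7 = 948 per arm, or 1896 in total against 1900 stated. The figure reproduces, and this point does not alter it. The 30% in it is an allowance for dropout; the protocol does not say whether that means stopping drug or leaving the study.

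**Scale of the gap.** No drug-discontinuation rate is given, so the share who stop and still return is an assumption:

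- 10%: 0.10 × 1900 = 190 subjects
- 20%: 0.20 × 1900 = 380 subjects
- 30%: 0.30 × 1900 = 570 subjects

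For staging the numbers are smaller. Subjects with dementia at baseline are outside the endpoint. If the cap of about 25% in the study design section were filled, and stopping did not depend on baseline stage, multiplying by 0.75 gives about 143, 285 and 428. Those who convert by Visit 15 are events and also drop out of the count.

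**The exception for FAQ.** Footnote b waives the return visit if it falls within 8 days after ED or within ±8 days of Visit 14 or 15, where FAQ is done anyway. That covers 8 + 17 + 17 = 42 possible stopping days. If stopping times were uniform over 728 days (an assumption), 42 / 728 = 5.8% of stoppers would have Month 24 covered.

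**The exception for staging.** A subject who stops in the last 84 days is staged at Visit 15 at or after Month 24. On the same assumption that is 84 / 728 = 11.5%.

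**The case against.** The best reply is that this is an ambiguity, not an omission. Section 9.5.5 promises efficacy assessment without limit. The efficacy description in the Amendment 04 text (Section 9.5.1.3.1) counts FAQ among the efficacy scales, and footnote a of Table 5 applies the Visit 7 to 13 windows to these return visits. A site could reasonably perform FAQ, and perhaps staging. In addition, the Amendment 05 text at hand starts at the schedule of assessments, so its earlier sections cannot be checked for a fuller list. That caveat stands. But footnote b is the only itemised instruction available, the Amendment 04 version of the footnote has the same efficacy list, and shared windows fix timing, not content. At best, sites will differ.

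Several stronger readings are tempting and are not supported:

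- *The intent-to-treat analysis loses its off-drug data.* The sentence "The primary analysis will be based on an intent to treat philosophy without regard to adherence to treatment" is written for the primary analysis, and CDR is on the list. It bears on FAQ only through the shared model and analysis set.
- *All off-drug data are lost.* FAQ at ED, Visit 14 and Visit 15 and staging at ED and Visit 15 remain. The loss is the 12- and 24-month values.
- *Every stopper is censored about 12 weeks after the last dose.* Those who convert by Visit 15 are events, and those demented at baseline are not in the model.
- *The 30% dropout allowance gives the number of stoppers, and hence a standard-error or person-time penalty.* The allowance is not a stopping rate. The MMRM also uses each stopper's other FAQ values, so a ratio based on completers alone would overstate the loss of precision.

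It is also fair to say that both endpoints lie outside the key secondary testing sequence.

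**Conclusion.** The point holds as a limited and inexpensive improvement. As itemised, Month-24 FAQ is missing for most subjects who stop drug and return, and staging ends at Visit 15 at the latest for the great majority of them. The affected number cannot be fixed from the protocol: 190, 380 or 570 of 1900 for FAQ under assumed stop-and-return shares of 10%, 20% or 30%, less the few per cent covered by the skip rule, and fewer for staging. Whether the censoring in the dementia analysis is informative depends on why subjects stop, which is not known in advance. The primary endpoint keeps its return-visit CDR. The key secondary endpoints (ADCOMS and amyloid PET SUVR) are neither FAQ nor staging, and they are unaffected.

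**What to change.** In Table 5 footnote b, add FAQ and disease staging, with the existing central review and adjudication, to the 12- and 24-month assessments of subjects who stopped drug. Align Section 9.5.5 by giving the same list or referring to the footnote. If the omission is deliberate, state instead that these two endpoints follow stoppers only to Visit 15, and define the estimand to match.

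The cost is a slightly longer visit. FAQ is a 10-item partner rating, the partner already contributes to the CDR at these visits, and partner input by telephone is allowed where the investigator finds it suitable. One limitation remains: staging at only 12 and 24 months fixes an off-drug conversion date only to within the interval between staging visits, coarser than the 3-monthly staging on schedule, and the Cox analysis should take account of that.

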Blood samples for clinical chemistry, hematology, and coagulation (revised per Amendment 02)	X	X	X	X	X	X	X	X	X	X	X	X	X	X	X	X	X
Urine sample for dipstick urinalysis ^j	X	X	X	X	X	X	X	X	X	X	X	X	X	X	X ^c	X	X
Blood sample for immunological assessments, (revised per Amendment 02) ^{ee}	X	X	X	X	X	X	X	X									
PBMCs for storage and testing required (revised per Amendment 05)	X					X		X				X	X				
Urine pregnancy test (females of CBP only) ^k	X		X	X	X	X	X	X	X	X	X	X	X	X	X ^{dd}	X	X

Table 5 Schedule of Procedures/Assessments in Study E2609-G000-302 (Revised per Amendments 04 and 05)

Phase Period	Randomization														Follow-Up		UNS Visit ^d
	Treatment												ED ^b	14 ^c	15 ^c		
Visit ^a	2	3	4	5	6	7	8	9	10	11	12	13	ED ^b	14 ^c	15 ^c		
Day	1	15	29	57	85	183	274	365	456	547	638	729		757	813		
Week	1	3	5	9	13	27	40	53	66	79	92	105		109	117		
Weeks elapsed since 1st dose	0	2	4	8	12	26	39	52	65	78	91	104		108	116		
Nominal months elapsed since 1st dose	0		1	2	3	6	9	12	15	18	21	24		25	27		
Procedures/ Assessments																	
Blood sample for viral characterization ^l	X																
Blood sample for storage for immune status ^m	X		X		X	X		X				X	X	X	X	X	
MMSE ⁿ	X					X		X		X		X	X	X	X		
CDR ⁿ	X				X	X	X	X	X	X	X	X	X	X	X		
ADAS-cog14 ⁿ	X					X		X		X		X	X	X	X		
FAQ ⁿ	X					X		X		X		X	X	X	X		
Disease Staging ^o					X	X	X	X	X	X	X	X	X		X		
NPI-10	X					X		X		X		X	X		X ^{hh}		
C-SSRS	X	X ^{gg}	X ^{gg}	X ^{gg}	X ^{gg}	X ^{gg}	X ^{gg}	X ^{gg}	X ^{gg}	X ^{gg}	X ^{gg}	X ^{gg}	X	X		X ^{dd}	
Clinical assessment of suicidal thinking and behavior ^p		X	X	X	X	X	X	X	X	X	X			X	X ⁱⁱ	X	
EQ-5D ^q						X		X		X		X	X				
QOL-AD ^r						X		X		X		X	X				
Zarit's Burden Interview of study partner						X		X		X		X	X				
MRI including vMRI and fMRI ^s								X				X	X				
Amyloid PET (optional substudy) ^t								X				X	X		X ^{cc}		
Tau PET (optional substudy) ^u												X	X		X ^{cc}		

Table 5 Schedule of Procedures/Assessments in Study E2609-G000-302 (Revised per Amendments 04 and 05)

Phase Period	Randomization															UNS Visit ^d
	Treatment												Follow-Up			
Visit ^a	2	3	4	5	6	7	8	9	10	11	12	13	ED ^b	14 ^c	15 ^c	
Day	1	15	29	57	85	183	274	365	456	547	638	729		757	813	
Week	1	3	5	9	13	27	40	53	66	79	92	105		109	117	
Weeks elapsed since 1st dose	0	2	4	8	12	26	39	52	65	78	91	104		108	116	
Nominal months elapsed since 1st dose	0		1	2	3	6	9	12	15	18	21	24		25	27	
Procedures/ Assessments																
Telephone contact ^v		X	X		X	X		X		X		X	X			

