Blood samples for PK ^w		X	X		X	X		X		X		X	X			
Blood samples for PD and exploratory biomarkers ^x	X	X	X		X	X		X		X		X	X	X	X	
CSF sampling for PK and PD (optional substudy) ^y												X	X		X ^{cc}	
Adverse events ^{ff}	X	X	X	X	X	X	X	X	X	X	X	X	X	X	X	X
Sleep/Dream Questionnaire ^z	X	X	X	X	X	X	X	X	X	X	X	X	X	X	X	X
Possible Drug Abuse Potential Form/ Questionnaire ^{aa}	X	X	X	X	X	X	X	X	X	X	X	X	X	X	X	X
Randomization	X															
Dispense study drug	X ^{bb}	X	X	X	X	X	X	X	X	X	X				X ^{dd}	

Notes

ADAS-cog14 = Alzheimer’s Disease Assessment Scale - Cognitive subscale (14 items), AE = adverse event, CBP = child-bearing potential, CDR = Clinical Dementia Rating scale, CMV = cytomegalovirus, CNS = central nervous system, CSF = cerebrospinal fluid, C-SSRS = Columbia Suicide Severity Rating Scale, ECG = electrocardiogram, ED = Early Discontinuation, EQ-5D = EuroQol-5 Dimensions, FAQ = Functional Assessment Questionnaire (also known as the Functional Activities Questionnaire), fMRI = functional MRI (to be performed task free at resting state), HSV1 = herpes simplex virus 1 (orolabial herpes), HSV2 = herpes simplex virus 2 (genital herpes), INR = International Normalized Ratio, LP = lumbar puncture, MMSE = Mini Mental State Examination, MRI = magnetic resonance imaging, NPI = Neuropsychiatric Inventory, PBMC = peripheral blood mononuclear cell, PD = pharmacodynamics, PET = positron emission tomography, PK = pharmacokinetics, QOL-AD = Quality of Life in Alzheimer’s Disease, QTcF = QTc interval calculated using Fridericia’s formula, UNS = unscheduled, vMRI = volumetric MRI.

a: A window of ±3 days will be permitted for Visits 3 and 4. A window of ±7 days will be permitted for Visits 5 and 6. A window of ±10 days will be permitted for Visits 7 to 13 inclusive (including for subjects who discontinue study drug early but who return for clinical assessments at 12 and 24 months). These windows should be calculated from Day 1. A window of ±3 days calculated from the last dose will be permitted for the Follow-up Visits. If use is made of the permitted visit windows, every effort should be made to bring the subject back in line with the “weeks elapsed since 1st dose” at subsequent visits.

Table 5 Schedule of Procedures/Assessments in Study E2609-G000-302 (Revised per Amendments 04 and 05)

Phase Period	Randomization															
	Treatment												ED ^b	Follow-Up		
Visit ^a	2	3	4	5	6	7	8	9	10	11	12	13	ED ^b	14 ^c	15 ^c	UNS Visit ^d

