9.7.1.1.4 EXPLORATORY ENDPOINTS

The exploratory endpoints of the study are:

- Time to change of concomitant AD treatment (ie, dose increase and/or initiation of treatment with AChEI or memantine after randomization) by 24 months
- The proportion of subjects at 24 months who received dose increases and/or initiation of treatment with AChEI or memantine after randomization
- The rate of change over time (mean slope) based on NPI-10 item score over 24 months
- Change from baseline in NPI-10 item at 24 months
- Change from baseline in EQ-5D (subject self-reported, study partner self-reported, and subject measured by proxy) and QOL-AD (subject and study partner) at 24 months
- Change from baseline in Zarit's Burden Interview at 24 months

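### Table 5 footnote b lets Visit 14 or 15 replace an early discontinuer's 12- or 24-month visit, but EQ-5D, QOL-AD and Zarit are not scheduled at either follow-up visit

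*Protocol*

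**What the plan says.** Three parts of the Protocol bear on this, all in the current (Amendment 05) text.

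- **What is due at the return visits.** Table 5 footnote b asks subjects who stop study drug before 12 months to return at 12 and 24 months, and those who stop later to return at 24 months. It names MMSE, CDR and ADAS-cog14 for these visits and adds that "quality of life (EQ-5D, QOL-AD and Zarit’s Burden Interview) will be assessed along with concomitant medications".
- **When they may be skipped.** The same footnote states: "These 12 and 24 month clinical assessment visits do not need to be attended if they fall within 8 days (visit window". That half of the sentence concerns the ED Visit. The other half extends the waiver to return visits falling "within ±8 days of either of the Follow-up Visits (Visit 14 and Visit 15". The timing of those visits is also given there: "Follow-up Visits will be scheduled 4 and 12 weeks after the last dose of study drug (Visit 14 and Visit 15, respectively".
- **What is done at Visits 14 and 15.** In the body of Table 5, CDR, MMSE and ADAS-cog14 are marked at ED, Visit 14 and Visit 15. The EQ-5D and QOL-AD rows and the row "Zarit's Burden Interview of study partner" are marked at Visits 7, 9, 11, 13 and ED only. Section 9.5.5 describes the purpose of the follow-up visits in the same spirit: "These Follow-up Visits will be conducted to monitor efficacy and safety parameters after early withdrawal from the study or discontinuation of study drug".

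Section 9.7.1.1.4 lists change from baseline in EQ-5D and QOL-AD at 24 months among the exploratory endpoints, and likewise "Change from baseline in Zarit's Burden Interview at 24 months".

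**The concern.** A rule that lets one visit stand in for another makes sense only if the replacing visit collects what the replaced one would have collected. Here it does so for the efficacy scales and not for the quality-of-life scales. A site that follows the footnote and the table exactly will see the subject close to Month 24, complete the CDR, and have no instruction to give EQ-5D, QOL-AD or Zarit, although the footnote itself requires them at Month 24.

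The gap arises only in subjects who have stopped study drug. At stake is part of the off-drug follow-up for the 24-month quality-of-life and partner-burden endpoints. A statistical analysis plan cannot recover values that the schedule did not collect, so the place to correct it is the schedule.

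**Working it through.** The plan gives no figure on this point, so there is none to reproduce. The check has three steps.

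**1. Table 5 read column by column against footnote b**

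| Instruments | Due at the return visit (footnote b) | ED | Visit 14 | Visit 15 |
|---|---|---|---|---|
| CDR, MMSE, ADAS-cog14 | yes | marked | marked | marked |
| EQ-5D, QOL-AD, Zarit | yes | marked | not marked | not marked |

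The ED half of the waiver loses nothing. The Visit 14/15 half omits the three quality-of-life instruments. Nothing else in the text at hand adds them to Visits 14 or 15. The Amendment 04 text in the same file (there Table 4 and its footnote b) shows the same pattern, so this is not an accident of one table's layout.

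**2. Which stop dates are affected**

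Inputs: Month 24 is Day 729 (Table 5, Visit 13). Visit 14 is 28 days and Visit 15 is 84 days after the last dose. The waiver is ±8 days. Let L be the day of the last dose, with follow-up visits at their nominal times.

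- Through Visit 14: |L + 28 − 729| ≤ 8, so L is from Day 693 to Day 709 (17 days).
- Through Visit 15: |L + 84 − 729| ≤ 8, so L is from Day 637 to Day 653 (17 days).

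Example: L = 645 gives 645 + 84 = 729. Visit 15 falls on the Month 24 target day itself, the 24-month visit may be skipped, and no quality-of-life instrument is scheduled.

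The same calculation for Month 12 (Day 365) gives last doses on Days 329-345 and 273-289.

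The nearest scheduled quality-of-life value is the ED Visit, 0 to 7 days after the last dose. Its distance from Day 729 is:

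- Visit 14 route: 729 − 709 − 7 = 13 days to 729 − 693 = 36 days.
- Visit 15 route: 729 − 653 − 7 = 69 days to 729 − 637 = 92 days.

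**3. Illustrative count at Month 24**

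Inputs: 1900 subjects and 30% dropout (Section 9.7.2). Two assumptions are not in the document: that the 30% is the share who stop drug but stay in follow-up, and that stop dates are spread evenly over Days 1-729.

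- Discontinuers: 0.30 × 1900 = 570.
- Share with a stop date in an affected band: (17 + 17)/729 = 34/729 = 4.7%.
- Affected: 570 × 34/729 = 26.6, about 27, which is 26.6/1900 = 1.4% of those randomized.

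The count scales directly with the share of those discontinuers who remain in follow-up: about 27 if all do, 13 if half do, 7 if a quarter do. Each 10 percentage points of drug discontinuation with continued follow-up contributes 0.10 × 1900 × 34/729 = 8.9 subjects.

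**The case against.** The mismatch between footnote and table cannot be argued away, but several things limit it.

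- **Only exploratory endpoints are affected.** CDR is done at Visits 14 and 15, so the primary endpoint is untouched. MMSE, ADAS-cog14 and FAQ are also marked there. This stands.
- **The values are at risk and not necessarily lost.** The footnote says the visits need not be attended. It does not forbid attending, or completing the questionnaires. A reader might infer that the data are lost in every such case; the text does not go that far.
- **A recent value usually exists.** ED includes all three instruments. Section 9.7.1.6.3 names a repeated-measures model among the possible methods, and such a model can use earlier values. It also names ANCOVA, so whether the ED value would contribute is open. A reader might infer that the quality-of-life analysis becomes materially more on-drug. Nothing in the document shows that a gap of this size would do so, and the intent-to-treat statement in Section 9.7.1.6.1 is made for the primary CDR-SB analysis.
- **A larger count is tempting.** Adding Month 12 gives 570 × 68/729 = 53 subjects. The quality-of-life endpoints are defined only at 24 months, so the Month 12 half touches no stated endpoint.
- **The two windows need not conflict.** Footnote a states: "A window of ±10 days will be permitted for Visits 7 to 13 inclusive (including for subjects who discontinue study drug early". A reader might infer a contradiction with the 8 days in footnote b. Footnote a governs when a return visit may take place, and footnote b when it may be skipped because another visit is near. Both can stand. Only the parenthetical label in footnote b, which calls the 8 days the visit window, is inconsistent.

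**Conclusion.** The point holds as a small, real inconsistency between footnote b and Table 5. The footnote requires EQ-5D, QOL-AD and Zarit at the return visits of early discontinuers, and the same footnote lets those visits be replaced by visits at which none of the three is scheduled. With follow-up visits at their nominal times, last doses on about Days 637-653 or 693-709 leave no scheduled Month 24 quality-of-life value in a subject who attends within 8 days of the target.

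The size is modest: about 27 of 1900 (1.4%) at Month 24. That figure is an illustration resting on two assumptions the document does not make, namely that 30% stop drug evenly over time and that all of them remain in follow-up. It falls if many of them leave the study, because they would then have no Month 24 visit to waive. The inconsistency itself does not depend on the count. Sample size, power, alpha and the primary analysis are unaffected. It is worth correcting because the correction is easy, not because it threatens the trial's conclusions.

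**What to change.** Amend footnote b so that Visit 14 or Visit 15 may replace the 12- or 24-month visit only if EQ-5D, QOL-AD and Zarit are completed at it and recorded as the Month 12 or Month 24 assessment. Mark the three rows of Table 5 conditionally at Visits 14 and 15 with a reference to that footnote. The ED half of the waiver can stay as it is.

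As a minor tidy-up, remove the label in footnote b that calls the 8 days a visit window, since footnote a sets ±10 days for these visits.

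The cost is a wording change and a slightly longer follow-up visit for the few subjects concerned, who are attending anyway. Section 9.5.1.6 (Amendment 04 text) already allows the study partner's part to be done by telephone where the investigator finds that suitable.
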